#### **12.1.3 Efficacy Analysis**

The intent-to-treat approach will be used. Baseline characteristics will be described using mean and standard deviation for continuous variables and medians and ranges for discrete variables. The primary efficacy variable of comparing PMA versus placebo will be undertaken by quantifying the instrument-assessment scores of each study subject in each of the two therapeutic arms of the investigation. The p-value, least square (LS) treatment means, difference between the LS treatment means, and 95% confidence intervals for the treatment differences will be presented. The success of blinding will be assessed by asking the patient and staff which treatment set they thought they were getting, i.e. active treatment or placebo. The results will be recorded at each study visit.

Total Nasal Symptoms Score (TNSS) and the Mini-RQLQ attached in Appendix F will be used to evaluate clinical efficacy. TNSS along with rescue medication use is recorded at home on a daily

card as shown in Appendix K. Daily scores will only be recorded on weeks 2, 10, and 14. The mini-RQLQ will be recorded in person at screening, during each study visit, and at followup. The correct use of the TNSS survey is to score 0-12 based on symptoms reported that day while the mini-RQLQ is scored 0-84 based on symptoms reported over the past week. Higher scores indicate worse symptoms.

The primary outcome measure is the average daily combined score (DCS) which is calculated by adding the average TNSS + average medication score as well as the mini-RQLQ at weeks 2,10 and 14.

Secondary outcomes will include the adverse events rate and TNSS between both groups using a one-tailed Fischer's exact test and/or unpaired t test.

Other outcomes include baseline characteristics, use of epinephrine, and drop out between both treatment groups I and II using a one-tailed Fischer's exact test and/or unpaired t test. Trend tests for comparison of both groups will be performed such as the Jonckheere-Terptsra trend test. A sum of Mann-Whitney-Wilcoxon tests may also be sensitive and reveal a mild trend. Other trend tests may also be used.

A Kaplan-Meier or similar product limit estimator function will also be used to calculate the effect of treatment over time.

Medications commonly used to treat allergic rhinitis such as nasal steroids, antihistamines, ophthalmologic antihistamines, cromolyn, azelastine, decongestants and other OTC allergy medications will be stopped during the 14 day washout period. Patients must abstain from using these medications for the duration of the study, however rescue medications will be offered in a predetermined manner as follows. At each study visit the patient will be asked subjectively if symptoms are adequately controlled. If symptoms are uncontrolled then medications will be added in the following stepwise fashion according to Appendix I. Rescue medications will not be increased after week ten.

Medication use is recorded daily at home during weeks 2, 10, and 14 and at each bi-weekly study visit so that adjustments can be made. Each allergy rescue medication will be assigned a numerical score as per Appendix I. We expect that most subjects will have daily medication scores between 0-6.

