## **5.0 STUDY DESIGN AND METHODS**

### **5.1 Study Design**

This is a phase 2 proof of concept study. It is being undertaken to characterize and quantify the clinical difference in signs and symptoms that may evolve when subjects with active SAR/PAR are administered a sub-cutaneous form of immunotherapy in a double-blind, prospective, controlled six weeks study wherein a PMA is compared with saline placebo.

Randomization to active PMA versus placebo treatment is on a 1 to 1 ratio. A double-blind study design is used to minimize outcome bias. Randomization measures to minimize bias at study entry include computerized random assignment of treatment versus placebo vials.

Subjects who are receiving nasal steroids for their SAR/PAR at screening may continue in the screening process if they agree to discontinue their therapy and commence a 14 day wash-out period of their medication prior to receiving active/placebo immunotherapy. Potential study subjects who, at screening, are not on active treatment for their SAR/PAR and asthma may enter directly into the investigation provided they fulfil entry and exclusion criteria and screening testing requirements.

The population to be studied consists of male and female adults aged 18 years to 65 years who are actively manifesting SAR/PAR have a score of at least 28 on the mini-RQLQ and 6 on the TNSS scale.

[figure not shown]
The active treatment phase of the study will be for six weeks with a safety followup assessment at 30 days post-treatment. No interim analysis is planned.

The study immunotherapy that will be evaluated in this study is a new innovative proprietary mixture of FDA approved allergens which has been clinically developed and evaluated, during the past three decades, in some 20,000 patients by the inventor of the mixture (see 3.2). In clinical evaluation this patented antigen mixture has provided clinical symptomatic relief to patients with SAR/PAR in as brief a period as three administrations of immunotherapy injections and has an observed overall success rate of approximately 80 to 90 percent of such treated subjects.

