### **6.1 Inclusion Criteria**

1. In the opinion of the investigator, the subject is capable of understanding and complying with protocol requirements.
2. The subject signs and dates a written, informed consent form prior to the initiation of any study procedures.
3. The subject is a male or a non-pregnant, non-lactating female between the ages of 18 and 65.
4. The study subject is currently experiencing active symptoms and signs of moderate to severe PAR with or without SAR component defined as score of at least 28 on the RQLQ and 6 on the TNSS scale. Scores will be determined on the first and second visit (after the 14 day medication washout period). Both scores exceeding their threshold on either day will qualify.
5. Skin test strongly positive (wheal at least 5mm diameter and 2mm greater than negative control) to at least 6 of 48 allergy skin prick tests including at least one species of dust mite.

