#### **8.3.2 Study Entrance Randomization**

Study Randomization will take place on study day 1 (Visit 1). The following procedures will be performed and documented during Study Randomization:

- If the subject has satisfied all of the inclusion criteria and none of the exclusion criteria for randomization and the investigator deems the laboratory screening and skin testing are acceptable for continuance in the investigation, the subject should be randomized using the randomization sequence provided by the sponsor.
- Subjects will receive their first sub-cutaneous administration of immunotherapy with dose vial #5.
- The procedure for documenting Screening failures is provided in Section 8.1.11.

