## STUDY DESIGN AND METHODS

### Study Design

This is a phase 2 proof of concept study. It is being undertaken to characterize and quantify the clinical difference in signs and symptoms that may evolve when subjects with active seasonal or perennial allergic rhinitis (SAR/PAR) are administered a sub-cutaneous form of immunotherapy in a double-blind, prospective, controlled six weeks study wherein a proprietary mixture of FDA approved allergens (PMA) is compared with saline placebo.

Randomization to active PMA versus placebo treatment is on a 1 to 1 ratio. A double-blind study design is used to minimize outcome bias. Randomization measures to minimize bias at study entry include computerized random assignment of treatment versus placebo vials.

Subjects who are receiving nasal steroids for their SAR/PAR at screening may continue in the screening process if they agree to discontinue their therapy and commence a 14-day wash-out period of their medication prior to receiving active/placebo immunotherapy. Potential study subjects who, at screening, are not on active treatment for their SAR/PAR and asthma may enter directly into the investigation provided they fulfil entry and exclusion criteria and screening testing requirements.

The population to be studied consists of male and female adults aged 18 years to 65 years who are actively manifesting SAR/PAR have a score of at least 28 on the mini-RQLQ and 6 on the TNSS scale.

[figure not shown]
The active treatment phase of the study will be for six weeks with a safety follow-up assessment at 30 days post-treatment. No interim analysis is planned.

The study immunotherapy that will be evaluated in this study is a new innovative proprietary mixture of FDA approved allergens which has been clinically developed and evaluated, during the past three decades, in some 20,000 patients by the inventor of the mixture (see 3.2). In clinical evaluation this patented antigen mixture has provided clinical symptomatic relief to patients with SAR/PAR in as brief a period as three administrations of immunotherapy injections and has an observed overall success rate of approximately 80 to 90 percent of such treated subjects.

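### The plan allows direct entry without washout but does not say when these subjects are first dosed, so their week 2 baseline DCS may fall after the first injections

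*Combined protocol and SAP*

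**What the plan says.** **Entry routes.** Protocol 5.1 describes two. Subjects on nasal steroids must stop them for 14 days before immunotherapy. Subjects not on active treatment at screening "may enter directly into the investigation provided they fulfil entry and exclusion criteria and screening testing requirements". The SAP (Study Design) repeats the second route: such subjects "are not on active treatment for their SAR/PAR and asthma may enter directly into the investigation".

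**First dose.** Section 8.3.2 schedules randomization for study day 1, labelled Visit 1, and lists under the same step: "Subjects will receive their first sub-cutaneous administration of immunotherapy with dose vial #5". Elsewhere the first dose is at visit 2: 9.2.1.1 says so, Appendix H starts its injection schedule there, and Appendix A has washout in weeks 1-2 and visits 2-17 in weeks 3-11.

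**Eligibility.** Section 6.1 scores subjects at visits 1 and 2, describes visit 2 as following the washout, and adds: "Both scores exceeding their threshold on either day will qualify".

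**Diary and endpoint.** Section 12.1.3 states: "Daily scores will only be recorded on weeks 2, 10, and 14". The DCS is "calculated by adding the average TNSS + average medication score" from those weeks. SAP primary outcomes 1 and 2 are the DCS changes from visit 2 to visit 17 and from visit 2 to visit 18.

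**The concern.** The diary calendar suits one kind of subject: screened in week 1, washed out in weeks 1-2, first injected in week 3. For that subject week 2 lies just before visit 2, and weeks 10 and 14 contain visits 17 and 18. The direct-entry sentence describes a second kind of subject, and the diary has no track for them.

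If a direct entrant is injected before the end of week 2, some or all of the cards meant to give the baseline DCS are completed on treatment. The medication part is exposed too. A subject who keeps to the washout has a baseline medication score of 0, because rescue is offered only at study visits. A direct entrant already attending injection visits could have been stepped up on the Appendix I ladder. A diary not kept before the first injection cannot be recovered afterwards.

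**Working it through.** **Plan's own figure.** Section 12.3 gives 28 subjects for 80% versus 30% response, alpha 0.05 and 80% power. The two-sided pooled normal approximation gives 15 per arm, 30 in total, and 79.1% power at 14 per arm. The figure reproduces closely. It is for response proportions, not for a DCS mean.

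**Calendar assumptions.** Screening is on day 1; week w covers days 7(w-1)+1 to 7w; 16 injections (Appendix H) follow at gaps alternating 3 and 4 days, in either order. Cards are completed at bedtime (Appendix K), so an injection-day card counts as post-injection. Visit 18 is 30 days after the last injection (8.3.5). Diary weeks 2, 10 and 14 are then days 8-14, 64-70 and 92-98.

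**Baseline cards, start on day 1.** Injections fall on days 1, 4, 8, 11, ... or 1, 5, 8, 12, .... Injections given by each card of days 8-14: 3, 3, 3, 4, 4, 4, 4 or 3, 3, 3, 3, 4, 4, 4. No card is pre-treatment.

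**Pre-treatment cards by day of first injection**

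| First injection | Pre-treatment cards in week 2 |
|---|---|
| Days 1-8 | 0 of 7 |
| Days 9-14 | 1 to 6 of 7 |
| Day 15 or later | 7 of 7 |

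**Later diaries.** The 15 gaps sum to 8×3 + 7×4 = 52 or 8×4 + 7×3 = 53 days. For starts on days 1-7 the last injection is on days 53-60, so the week 10 diary begins 4 to 11 days after it. Visit 18 is on days 83-90, so the week 14 diary begins 2 to 9 days after the final visit. For a start on day 15 the last injection is on day 67 or 68 and visit 18 on day 97 or 98, both inside their diary weeks.

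**Medication score, start on day 1.** If symptoms are reported uncontrolled at every visit, the Appendix I steps are 1, 2, 4 and 6 points. The week 2 mean is (3×4 + 4×6)/7 = 5.1 or (4×4 + 3×6)/7 = 4.9. If rescue starts at the second visit it is (3×2 + 4×4)/7 = 3.1 or (4×2 + 3×4)/7 = 2.9. If symptoms are controlled throughout it is 0. The range is therefore 0 to about 5.

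**Early dose.** Dose is taken as volume times nominal dilution (Appendix H). Each vial contributes 0.15 + 0.30 + 0.45 + 0.60 = 1.5 ml. First four injections: 1.5/625 = 0.0024. Total: 1.5 × (1/625 + 1/125 + 1/25 + 1/5) = 0.3744. The ratio is 0.64%.

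**Power, as illustration only.** The share f of direct entrants dosed early is not in the documents. A two-sided t test has 80% power at 14 per arm for a standardized difference d = 1.10; this d is back-solved, not stated in the plan. If these subjects are dropped from all 36 for want of a baseline:

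| Assumed f | Subjects with DCS change | Power at d = 1.10 |
|---|---|---|
| 0% | 36 | 89% |
| 10% | about 32 | 86% |
| 25% | 27 | 78% |
| 50% | 18 | 59% |

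If they are kept with a post-injection baseline, the difference shrinks by f×e, where e is the assumed share of the effect already present in week 2. With 28 analysed, f×e of 0, 6.25%, 12.5% and 25% gives power of 80%, 75%, 69% and 56%.

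**The case against.** Most of the protocol describes a single calendar. Section 1.2 has the subject abstain for two weeks and then return for the injection, with no exception. Section 8.3.1 places screening before the washout, 6.1 places visit 2 after it, and 9.2.1.1, Appendix A and Appendix H all make visit 2 the first injection. On that calendar week 2 is pre-treatment for everyone. The direct-entry sentence gives no dosing day and could mean only that these subjects have no medication to stop. Section 8.3.2 does not distinguish entry routes, and 8.3.3 numbers visits in a way that also conflicts with Appendix A, so the visit numbers in 8.3 may simply be unreliable. The qualifying rule in 6.1 concerns eligibility, not dosing.

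This defeats the stronger reading a reader might take, that direct entrants certainly have no pre-treatment DCS. The documents do not establish that. What stands is that the sentence, repeated in the SAP, is set against a washout required before immunotherapy, that 8.3.2 supports early dosing, and that nothing settles which rule governs.

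A reader might also infer bias between the arms. Entry route is fixed before treatment, so route-dependent medication scores mainly add variance. Bias toward no effect needs the drug to act within the first few injections. Section 5.1 claims relief "in as brief a period as three administrations of immunotherapy injections", but those injections carry a very small part of the nominal dose, so e may be near 0.

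TNSS (Appendix A) and medication use (12.1.3) are also recorded at clinic visits. They could serve as a stand-in, but a single-day record is not the averaged diary score, and no text names it as the baseline or says it is taken before the injection.

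**Conclusion.** The point holds as a conflict between operational rules that leaves the DCS baseline undefined for one entry route. If direct entrants are dosed before the end of week 2, their baseline is partly or wholly post-injection, and for week 1 starts the later diaries no longer match visits 17 and 18. If they follow Appendix A, the baseline is sound, and 5.1, 8.3.2 and the SAP are wrong. Text has to change either way.

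Two of the four primary outcomes are exposed, and the secondary TNSS changes too if they are taken from the diary. The mini-RQLQ outcomes are not affected provided visit 2 is the first-injection visit.

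The documents do not support a conclusion that the trial is underpowered for this reason: the share of early-dosed direct entrants is unknown, and at an assumed 10% of 36 power stays above the planned 80%. The main effect is missing or mismeasured baselines and added variance. The calendar results rest on the assumed injection spacing and on study weeks counted from screening.

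**What to change.** In 5.1, 12.1.3 and the SAP, state that every subject, washed out or not, completes the daily card on the 7 days before the first injection, which is visit 2 and not earlier than study day 8. Time the later cards from the first injection, in treatment weeks 8 and 12, so that they contain visit 17 (treatment day 53 or 54) and visit 18 (treatment day 83 or 84). Offer rescue medication only from visit 2. In 8.3.2, replace study day 1 and Visit 1 with visit 2, and align Appendix A.

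Alternatively, delete the direct-entry sentence from 5.1 and the SAP so that all subjects follow Appendix A; 8.3.2 still needs the same correction.

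This is a cheap improvement: wording only, with the same number of cards. A washed-out subject starting on day 15 keeps the same diary days (8-14, 64-70 and 92-98). The downside is that direct entrants wait one week under the first option, or two under the second, before their first injection.

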#### **12.1.4 Safety Analysis**

Overall safety and tolerability will be assessed by evaluating the incidence of TEAE, laboratory tests, vital signs, and other safety variables. Treatment-emergent adverse events will be defined as any AEs, regardless of relationship to study immunotherapy, that occur on or after the first double blind immunotherapy administration date and up to 30 days after the last dose date of the double-blind immunotherapy and will be assigned to the treatment at the time of the event.

Treatment-emergent adverse events will be summarized using the full analysis set. Adverse events will be summarized using the MedDRA coding dictionary. In general, AEs will be tabulated at each of the following levels: overall summary (subject with at least 1 AE), the MedDRA system organ class (SOC) and the MedDRA preferred term (PT). Tabulations at each level of a term will present count (n) and percentage of subjects reporting any event for that term. Subjects reporting more than one occurrence for the term (level) being summarized will be counted only once and assigned to the drug assignment at time of the event.

Laboratory test variables will be summarized by active PMA or placebo assignment and study visit using descriptive statistics. Laboratory data collected from baseline and up to 7 days after a subject's last dose of study immunotherapy will be included in the analysis. Markedly abnormal laboratory values will be determined and listed by study group. The number and percentage of subjects with marked abnormality in each of the laboratory parameters will be presented.

Descriptive statistics will be used to summarize vital signs by treatment group and study visit. Vital sign data collected from baseline and up to a subject's last dose of study immunotherapy will be included in the analysis.

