### **6.4 Criteria for Discontinuation or Withdrawal of a Subject**

The primary reason for discontinuation or withdrawal of the subject from the study or study medication should be recorded in the CRF using the following categories. For screen failure subjects, refer to Section 8.1.11.

1. Pretreatment event (PTE) or adverse event (AE). The subject has experienced a PTE or AE that requires early termination because continued participation imposes an unacceptable risk to the subject's health or the subject is unwilling to continue because of the PTE or AE.
2. Significant protocol deviation. The discovery postrandomization or after the first dose of study immunotherapy that the subject failed to meet protocol entry criteria or did not adhere to protocol requirements, and continued participation poses an unacceptable risk to the subject's health.
3. Lost to follow-up. The subject did not return to the clinic and attempts to contact the subject were unsuccessful. Attempts to contact the subject must be documented.
4. Voluntary withdrawal. The subject (or subject's legally acceptable representative) wishes to withdraw from the study. The reason for withdrawal, if provided, should be recorded in the

CRF. All attempts should be made to determine the underlying reason for the withdrawal and, where possible, the primary underlying reason should be recorded.

5. Study termination. The sponsor, IRB, or regulatory agency terminates the study.
6. Pregnancy. The subject is found to be pregnant.

Note: If the subject is found to be pregnant, the subject must be withdrawn immediately. The procedure is described in Section 8.1.10.

7. The investigator has determined that continued participation would pose an unacceptable risk to the subject.

Note: After the 30 minute wait period, subjects that develop local swelling at the site of the injection greater than 50mm diameter will have their next dose decreased by one step. Subjects having a Grade 1-2 systemic reaction will have their next injection decreased by two steps. Systemic reaction Grade 3 or more will require withdrawal from the study. Systemic reactions are defined by the World Allergy Organization anaphylaxis grading system (13).

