#### **9.1.3 Additional Points to Consider for PTEs and AEs**

An untoward finding generally may:

- Indicate a new diagnosis or unexpected worsening of a pre-existing condition. (Intermittent events for pre existing conditions underlying disease should not be considered PTEs or AEs.)
- Necessitate therapeutic intervention.
- Require an invasive diagnostic procedure.
- Require discontinuation or a change in dose of study medication or a concomitant medication.
- Be considered unfavorable by the investigator for any reason.
- PTEs/AEs caused by a study procedure (eg, a bruise after blood draw) should be recorded as a PTE/AE.

Diagnoses vs signs and symptoms:

- Each event should be recorded to represent a single diagnosis. Accompanying signs or symptoms should NOT be recorded as additional AEs. If a diagnosis is unknown, sign(s) or symptom(s) should be recorded appropriately as a PTE(s) or as an AE(s).

Pre-existing conditions:

- Pre-existing conditions (present at the time of signing of informed consent) are considered concurrent medical conditions and should NOT be recorded as PTEs or AEs. Baseline evaluations (eg, laboratory tests, ECG, X-rays etc.) should NOT be recorded as PTEs unless

related to study procedures. However, if the subject experiences a worsening or complication of such a concurrent condition, the worsening or complication should be recorded appropriately as a PTE (worsening or complication occurs before start of study medication) or an AE (worsening or complication occurs after start of study medication). Investigators should ensure that the event term recorded captures the change in the condition (eg, “worsening of...”).

- If a subject has a pre-existing episodic condition (eg, gout, epilepsy) any occurrence of an episode should only be captured as a PTE/AE if the episodes become more frequent, serious or severe in nature, that is, investigators should ensure that the AE term recorded captures the change in the condition from Baseline (eg “worsening of...”).

Worsening of PTEs or AEs:

- If the subject experiences a worsening or complication of a PTE after starting administration of the study medication, the worsening or complication should be recorded appropriately as an AE. Investigators should ensure that the AE term recorded captures the change in the condition (eg, “worsening of...”).

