- If the subject experiences a worsening or complication of an AE after any change in study medication, the worsening or complication should be recorded as a new AE. Investigators should ensure that the AE term recorded captures the change in the condition (eg, “worsening of...”).

Changes in severity of AEs /Serious PTEs:

- If the subject experiences changes in severity of an AE/serious PTE, the event should be captured once with the maximum severity recorded.

Preplanned surgeries or procedures:

- Preplanned procedures (surgeries or therapies) that were scheduled prior to signing of informed consent are not considered PTEs or AEs. However, if a preplanned procedure is performed early (eg, as an emergency) due to a worsening of the pre-existing condition, the worsening of the condition should be captured appropriately as a PTE or an AE. Complications resulting from any planned surgery should be reported as AEs.

Elective surgeries or procedures:

- Elective procedures performed where there is no change in the subject’s medical condition should not be recorded as PTEs or AEs, but should be documented in the subject’s source documents. Complications resulting from an elective surgery should be reported as AEs.

Insufficient clinical response (lack of efficacy):

- Insufficient clinical response, efficacy, or pharmacologic action, should NOT be recorded as an AE. The investigator must make the distinction between exacerbation of pre-existing illness and lack of therapeutic efficacy.

Overdose:

- Cases of overdose with the immunotherapy without manifested side effects are NOT considered PTEs or AEs, but instead will be documented on an Overdose page of the CRF. Any manifested side effects will be considered PTEs or AEs and will be recorded on the AE page of the CRF.

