#### 9.1.11 Action Concerning Study Medication

- Stop immunotherapy – the study immunotherapy is stopped due to the particular AE.
- Immunotherapy not changed – the particular AE did not require stopping the study immunotherapy.
- Unknown – only to be used if it has not been possible to determine what action has been taken.
- Not Applicable – the immunotherapy was stopped for a reason other than the particular AE eg, the study has been terminated, the subject died, dosing with the study immunotherapy was already stopped before the onset of the AE.

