## **Secondary Outcomes**

1. Total nasal symptoms score (TNSS)- Comparison of the delta visit 2 to visit 17 (change in score) between both treatment groups I and II using an unpaired t test.
2. TNSS - Comparison of the delta visit 2 to visit 18 (change in score) between both treatment groups I and II using an unpaired t test.
3. Adverse Events - Adverse events (AEs) were to be spontaneously reported or elicited during open-ended questioning, examination, or evaluation of a patient. Comparison of the rates of adverse events between both treatment groups I and II will be evaluated using a one-tailed Fischer's exact test.

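### Mandatory dose step-downs under section 6.4 appear to fit only the action code 'not changed', and no specified output counts them or the reactions that trigger them

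*Combined protocol and SAP*

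**What the plan says.** **Dosing rule.** The note at the end of protocol section 6.4 states that "subjects that develop local swelling at the site of the injection greater than 50mm diameter will have their next dose decreased by one step". It continues: "Subjects having a Grade 1-2 systemic reaction will have their next injection decreased by two steps". Grade 3 or higher leads to withdrawal. Both reductions are mandatory as worded.

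**AE guidance.** Among the marks of an untoward finding, section 9.1.3 lists "Require discontinuation or a change in dose of study medication or a concomitant medication". When severity changes, "the event should be captured once with the maximum severity recorded". Severity (9.1.5), relatedness (9.1.6), the action taken and seriousness (9.2.1.2) are recorded for each AE.

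**Action codes.** Section 9.1.11 has four: stop, not changed, unknown and not applicable. 'Not changed' applies when "the particular AE did not require stopping the study immunotherapy".

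**Planned output.** Section 12.1.4 sets out three levels: any AE, system organ class and preferred term. It says "Tabulations at each level of a term will present count (n) and percentage of subjects reporting any event for that term", and "Subjects reporting more than one occurrence for the term (level) being summarized will be counted only once". SAP secondary outcome 3 adds a "Comparison of the rates of adverse events between both treatment groups I and II" by a one-tailed Fisher test. Neither document names a table of dose reductions, of swelling above 50 mm or of systemic reactions by grade.

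**The concern.** The thresholds in section 6.4 are the protocol's own definition of an injection reaction serious enough to alter treatment. An action field that cannot record the alteration would put a reaction that forced a lower dose in the same category as one with no consequence. A count of dose reductions taken from that field would be zero whatever happened.

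The AE profile is a named secondary endpoint, and the placebo is built to resemble the active product locally. Section 7.1.1 (item 7.1.3, placebo set) adds histamine, with itch expected in about 20% of controls. The same text puts swelling and itch on active treatment at no more than 20%. Overall AE incidence, or itch incidence, could therefore be similar in the two arms by design. What could still differ is the size and grade of reactions and how often they force a step-down, and these are the items without a specified output.

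**Working it through.** The plan gives no computed figure on this point, so the main check sets its sections side by side.

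**Step 1. Match each 6.4 event to a 9.1.11 code.**

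| Event in 6.4 | Required action | Code whose definition fits |
|---|---|---|
| Swelling above 50 mm | Next dose one step lower | Not changed (no stop needed) |
| Systemic Grade 1-2 | Next dose two steps lower | Not changed (no stop needed) |
| Systemic Grade 3 or higher | Withdrawal | Stop |

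'Unknown' is reserved for cases where the action could not be determined. 'Not applicable' covers treatment stopped for some other reason. In the first two rows the action is known and treatment continues, so only 'not changed' is left.

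**Step 2. Look for the same information in the specified outputs.**

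- Any-AE, organ-class and preferred-term rows give occurrence per subject, not size, grade or dose action. A separate preferred term for swelling could show an imbalance in swelling, but not how many exceeded 50 mm.
- The 9.1.5 severity scale rates tolerability and interference with activities. A well-tolerated swelling above 50 mm would be mild, so a severity table alone would not stand in for the 6.4 thresholds.
- Vital signs, which include peak flow (8.1.5), are summarised by arm and visit. Epinephrine use and drop-out are compared by arm. Stopping for intolerance is summarised by arm, pooled with lack of efficacy. These bear mainly on systemic or treatment-ending reactions.
- Appendix J records vial and dose at each visit, and 9.2.1.2 item 5 asks for details of the suspected administration. Step-downs could be rebuilt from these, but no output does so.

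**Step 3. Scale.** Inputs: 36 subjects at 1:1, so 18 per arm; 20% as the upper bound for active subjects.

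- Ceiling on active subjects with swelling and itch: 0.20 × 18 = 3.6.
- Exact (Clopper-Pearson) 95% limits: 0/18 gives 0% to 1 − 0.025^(1/18) = 18.5%; 4/18 (22%) gives 6.4% to 47.6%.
- Illustration near the ceiling: 4/18 v 4/18 with any AE (one-tailed Fisher p = 0.65). That row is the same whether 0, 1, 2, 3 or 4 of the active subjects exceeded 50 mm. A row for swelling above 50 mm, with none on placebo, would run from 0/18 v 0/18 to 4/18 v 0/18.
- At the far end, 4/18 v 0/18, the two-sided Fisher p = 2 × C(18,4)/C(36,4) = 2 × 3,060/58,905 = 0.10.

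Even the most extreme split in this illustration is visible but not significant, so the added rows are for description.

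**The case against.** The strongest reply is that nothing has been lost. Severity, relatedness, seriousness and action are collected for every event. Section 12.1.4 is worded as a general rule and leaves room for other safety variables, and the SAP allows additional methods before database lock. Analysts would normally produce severity and relatedness tables without being told to. That stands. A reader might infer that the missing severity and relatedness tables are themselves an error in the plan. The documents do not support this: such tables are routine additions that remain open.

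A second reply is that 9.1.11 nowhere says a step-down is to be coded as not changed. That is also right. It is an inference from the definitions, and the AE page could carry another option.

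A third is that the illustration could be read as a forecast. It is not one. The 20% is a ceiling for active treatment, and section 9.1.4 reports a rate below 20% with mild to moderate swelling. Nothing in the documents suggests that all such swellings would exceed 50 mm. Preferred-term rows might also separate swelling from itch, depending on coding.

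What survives is narrower. As written, the code list has no correct entry for an action the protocol makes mandatory, and leave to add tables does not correct a wrongly coded field.

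**Conclusion.** The point holds and is minor. Sections 6.4 and 9.1.11 do not fit together: a required dose reduction falls by definition under 'not changed', and no specified output counts reductions or the reactions behind them. This rests on the code definitions as printed and on the AE page offering no further option.

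A reader might go on to infer that serious reactions would be hidden. The documents do not support that. Grade 3 or higher leads to withdrawal and so enters the drop-out comparison, though not split by grade; epinephrine use and vital signs are reported by arm; and the dose given stays on the visit form. The gap concerns reactions large enough to lower the dose but not to end treatment.

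In size, at most about 3.6 active subjects of 18 would be expected to have swelling and itch at all, and no significant contrast is expected. Efficacy conclusions are not affected.

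**What to change.** 1. Add a 'dose reduced' option to section 9.1.11, and confine 'not changed' to events after which the dose followed the schedule.
2. Add to section 12.1.4, with a reference in SAP secondary outcome 3, descriptive per-arm counts of subjects with any 6.4 dose reduction, with local swelling above 50 mm, and with a systemic reaction by grade. Give each an exact 95% confidence interval.
3. Record systemic grade and swelling diameter as structured items if the AE page does not already do so. This should be in place before data collection, because a diameter not measured at the visit may not be recoverable.
4. As routine good practice, tabulate treatment-emergent AEs by maximum severity and by relatedness.

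The cost is one added code, a few descriptive tables, one sentence in the SAP and, at most, a small CRF edit. Severity, relatedness and dose are already collected. The primary analysis and the sample size stay as they are.
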